4.0 INVESTIGATIONAL PLAN

4.1 Summary of Study Design

This is a Phase IIb, multicenter, placebo-controlled, randomized, double-blind, parallel-arm study to evaluate the efficacy and safety of two doses of CT-P27 (45 mg/kg and 90 mg/kg) in subjects with acute uncomplicated influenza A infection. This proof-of-concept study will provide dose-ranging information for the subsequent clinical development of the drug.

No study procedures will be performed prior to informing the subject about the study and obtaining written informed consent. However, any test result which was obtained within the allowed screening period can be used as screening data for subject's convenience. It is critical that subjects receive treatment with study drug no more than 48 hours after the onset of symptoms (window of +12 hours is allowed). For most subjects, obtainment of the informed consent form (ICF), screening for eligibility, randomization and treatment will occur on the same day. Though obtainment of the ICF may occur on the day prior to screening, randomization or treatment, it must be within 24 hours before the administration of study drug.

To be eligible for enrollment, subjects must have a positive test result for influenza A by a rapid influenza diagnostic test. At screening, nasopharyngeal swab samples will be collected for two times to be used for rapid influenza diagnostic test and virology assessment. The enrollment process is presented in [Figure 1](#).

[figure not shown]

Figure 1 Enrollment Process

Approximately 183 subjects with influenza A to be enrolled in the study will be randomly assigned to 1 of 3 groups, 45 mg/kg CT-P27, 90 mg/kg CT-P27, or placebo (approximately 70 subjects per CT-P27 treatment groups and 43 subjects in placebo group). Randomization will be stratified by flu vaccination history within a year (Yes vs No) and participation in PK sub-study (Yes vs No). A schematic diagram of subject assignment is presented in [Figure 2](#).

[figure not shown]
[figure not shown]

Figure 2 Schematic Diagram of Subject Assignment

All enrolled subjects will be given a single dose of 45 mg/kg CT-P27, 90 mg/kg CT-P27, or placebo intravenously over 90 minutes (± 15 minutes) on Day 1 and then followed by 110 days.

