10. If symptoms have not relieved up to Day 3, chest x-ray will be performed to determine presence of secondary complications of influenza A infection.
11. Treatment with study drug must occur no more than 48 hours after the onset of symptoms. If the adjustments of visit schedule is required, additional 12 hours can be allowed (Maximum onset of illness: 60 hours).
12. PK blood sampling at:
 - Day 1: pre-infusion (within 15 minutes prior to the beginning of study drug infusion), at the end of infusion (within 15 minutes after the end of study drug infusion), and 1 hour (±15 minutes) after the end of the study drug infusion.
 - Day 2: 24 hours (±4 hours) after the start of the study drug infusion.
 - Day 3: 48 hours (±4 hours) after the start of the study drug infusion.
 - Day 8: 168 hours (±4 hours) after the start of the study drug infusion.
 - Day 15 (±2 days), Day 29 (±5 days), Day 57 (±5 days), and Day 110 (±5 days)/EOS visit.
13. Day 1: prior to the study drug infusion.

14. On Day 1, vital signs (including blood pressure and heart rate, respiratory rate), body temperature and ECG will be assessed at the time points listed below, and the subject will be monitored continuously over the period for possible immediate hypersensitivity reactions.
- Vital sign and body temperature
 - Pre-infusion (within 15 minutes prior to the beginning of the infusion).
 - 30 minutes (± 15 minutes) after the beginning of the infusion.
 - Within 15 minutes after the end of the infusion.
 - 2 hour (± 15 minutes) after the end of the infusion.
 - Vital sign, body temperature and ECG
 - 1 hour (vital sign, body temperature: ± 15 minutes, ECG: $-30/+60$ minutes) after the end of the infusion.
- Emergency drugs and equipment suitable for assistance during anaphylactic reactions will be available during infusion with study drug.
15. When collecting the nasopharyngeal swabs, nasopharyngeal swabbing will be performed by trained site personnel. A nasopharyngeal swab sample will be obtained from all subjects up to Day 8 on the following schedule:
- Screening (Nasopharyngeal swab samples will be collected for two times to be used for rapid influenza diagnostic test and virology assessment.)
 - Day 2: 24 hours (± 4 hours) after the start of the study drug infusion.
 - Day 3: 48 hours (± 4 hours) after the start of the study drug infusion.
 - Day 5: 96 hours (± 4 hours) after the start of the study drug infusion.

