 - Day 8: 168 hours (± 4 hours) after the start of the study drug infusion.
16. Sponsor-supplied or agreed in advance rapid influenza diagnostic test material will be used. And if there is available test result confirmed as influenza A prior to obtaining written informed consent and that result was from the influenza diagnostic test which is agreed with Sponsor in advance, that test result can be allowed. At screening, testing must be performed within 24 hours before study drug administration. Subjects with a negative test result by rapid diagnostic test, who have onset of symptoms within 48 hours (window of $+12$ hours is allowed) before study drug administration, can be rescreened only once.
17. The Investigator or designee will perform a symptom-directed physical examination (which should include, at a minimum, the examination of ear, nose, throat, sinuses, and lungs) and assessment for potential complications of influenza.
18. The subject will record the results of the Flu-iiQ™ in the diary.
- Flu-iiQ™ will be recorded once by the subject at the screening visit and will be recorded twice a day (at approximately 12-hour intervals) from Day 1 to Day 8 (in the morning [between 6 and 10 AM, approximately] and in the evening [between 6 and 10 PM, approximately]).
19. Body temperature which a subject experiences in prior to screening will be collected and body temperature taken with any type of thermometer will be acceptable. However, from the screening period, Sponsor-supplied thermometer will be used.
- Temperature will be measured by subject; It will be recorded twice a day (at approximately 12-hour intervals) from Day 1 to Day 8 (in the morning [between 6 and 10 AM, approximately] and in the evening [between 6 and 10 PM, approximately]).
 - Temperature will be measured by site personnel at site: at screening, Day 1 (prior to infusion), Day 2 (± 4 hours), Day 3 (± 4 hours), Day 5 (± 4 hours) and Day 8 (± 4 hours).
 - These will be used for assessment of endpoint.
20. Use of all medications, from 30 days prior to randomization and up until Day 110/EOS visit, will be recorded in the subject's eCRF.
21. AEs will be collected from the date the informed consent form is signed until Day 110/EOS visit.
22. EOS visit will be done at Day 110. But if a subject is early terminated from the study, EOS visit will be done to assess safety parameters at any time.

Schedule of Assessments (Unscheduled Visits Subjects with suspicious ADE)

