6.1.2 Nasopharyngeal Swabs

The Sponsor will provide nasopharyngeal swabs for use during the study. Samples from these swabs will be used to obtain samples for qPCR and cell culture, to confirm influenza A infection and evaluate viral shedding and to assess genotype, phenotype, and to assess antiviral resistance.

A nasopharyngeal swab sample will be obtained from all subjects and will be collected for two times to be used for rapid influenza diagnostic test and virology assessment at screening. Nasopharyngeal samples will be obtained at each subsequent study visit: Day 2 (24 hours [± 4 hours] after the start of the study drug infusion), Day 3 (48 hours [± 4 hours] after the start of the study drug infusion), Day 5 (96 hours [± 4 hours] after the start of the study drug infusion), and Day 8 (168 hours [± 4 hours] after the start of the study drug infusion).

The time selected for taking the swabs will be similar at each study visit (e.g., in the morning (between approximately 6 A.M. and 10 A.M.) or in the evening (between approximately 6 P.M. and 10 P.M.)).

Under some circumstances additional nasopharyngeal swabbing may occur. If the subject meets the definition for suspicious ADE (see [Section 6.2.5](#)), the subject will have additional swabs taken (at scheduled or unscheduled visits, as necessary) until Day 8 (168 hours) after the day of ADE occurrence.

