5.1 General Analysis Considerations

The statistical analysis will be performed using [REDACTED]. Any deviations from the planned analysis as described in this SAP will be justified and recorded in the CSR.

The data documented and the clinical parameters measured in this study will be described using descriptive statistics (including number [n], mean, median, Standard Deviation (SD), minimum, and maximum) for continuous variables: minimum and maximum will be presented to the same number of decimal places as the raw data, mean and median will be presented to one more decimal place than the raw data, and SD will be presented to two more decimal places than the raw data. If the geometric mean is to be presented, it will be set to the same precision as the mean. However, geometric mean will not be calculated when minimum value from the data is zero. Percent Coefficient of Variation (CV%) will be presented to two decimal places. P-values will be rounded to three decimal places. If a p-value is less than 0.001 it will be reported as "<0.001". If a p-value is greater than 0.999 it will be reported as ">0.999".

Categorical data will be summarized using count and percentage in each category. Percentages will be presented to one decimal place. The percentage will be suppressed when the count is zero in order to draw attention to the non-zero counts. "Not done" and "Missing" category will be included to account for cases of no assessment and missing respectively even if they are not recorded in eCRF. The denominator for all percentages will be the number of subjects within the treatment group for the population of interest, unless otherwise indicated.

All data will be displayed in listings. Unless otherwise specified, listings will be sorted by the treatment group, subject number, and assessment date or visit date, if applicable. In cases where more ordering is required, other variables will be included in the sort order as applicable.

Baseline will be the latest available measurement prior to the start of the infusion of study drug.

When summarizing End-of-Study (EOS) visit, the early termination cases are excluded from the summary for EOS visit, but will be presented in data listings. Unscheduled results will not be included in the summary tables except for determining baseline or if unscheduled results are necessary to interpret data, but they will be presented in data listings.

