Viral shedding (titers) of swab samples based on qPCR and cell culture will be evaluated at the scheduled collection times. The listing will include titer results, whether the influenza A is confirmed and Area under the Curve (AUC) of viral loads. However, since cell culture results have information of both influenza A and B, the listing and tables for cell culture will present analysis results regardless of influenza type. Changes in viral shedding will be assessed as the change from baseline in \log_{10} vp/mL and \log_{10} TCID₅₀/mL for qPCR and cell culture respectively. If viral loads are lower than LLoQ (2.18 for qPCR), they will be treated as value without inequality sign. Whereas viral load lower than LLoQ for cell culture (0.75) will be considered as negative value and a negative value will be treated as 0. If the subtype of influenza A is "H1", "NA" or "Unknown", the virus titer from HA assay will be used for cell culture analysis. Otherwise, if the subtype is "H3", the virus titer from NP ELISA will be used.

These will be summarized for each treatment group and collection time.

The following analyses will also be performed:

- Summary of viral shedding results; percentage of subjects with positive/negative viral shedding at each visit (baseline, day 2, 3, 5, 8)
- Duration (in days) of viral shedding; from date/time of baseline assessment to last positive sample. Subjects with at least one positive sample after baseline will be included in the summary.

Statistical Analysis Plan

- AUC of viral levels; from date of baseline assessment to last measurable value of subjects who have at least one post-baseline result (including BLQ (Below the Limit of Quantification) and negative values). If there are BLQ or missing values between measurable values, they are assumed to fall linearly between measurable values.
- Change from baseline in descriptive statistics of viral shedding of Swab Samples; descriptive statistics of actual value and change from baseline for viral shedding of swab samples will be presented by treatment group at each visit.
- Mean viral load titer (log values)
Mean viral load titer for each scheduled time point will be plotted with the SD of mean value.

- Incidence of secondary complications of influenza

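### Viral shedding duration (SAP 10.2) treats subjects still positive at their last swab as finished and drops those who clear before Day 2, which can compress the difference between arms

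*SAP*

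**What the plan says.** SAP 10.2, under viral shedding, lists the output "Duration (in days) of viral shedding; from date/time of baseline assessment to last positive sample" and adds: "Subjects with at least one positive sample after baseline will be included in the summary". SAP 14.7 gives its form: Tables 14.2.11.x, descriptive statistics for qPCR and for cell culture, in the ITT and ITTI populations. No rule covers a subject whose last swab is positive, and the missing-data rules in SAP 10.3.2 do not mention shedding.

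The clock starts at baseline, which SAP 5.1 defines thus: "Baseline will be the latest available measurement prior to the start of the infusion of study drug". For virology this is the screening swab.

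Protocol Table 1, footnote 15, fixes the swabs: "A nasopharyngeal swab sample will be obtained from all subjects up to Day 8 on the following schedule", namely screening and 24, 48, 96 and 168 hours. The last entry reads "Day 8: 168 hours (± 4 hours) after the start of the study drug infusion".

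Swabbing can go on longer in one group. Protocol 6.1.2 provides further swabs "If the subject meets the definition for suspicious ADE", for 168 hours after the day of occurrence. Protocol 6.2.5 puts in that group anyone whose symptoms the investigator judges unresolved up to Day 8, and lets the cycle repeat.

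**The concern.** The end of shedding is an event time. For a subject positive at the final swab, all that is known is that shedding outlasted that swab. Recording the swab time as a completed duration treats a right-censored value as exact. The same happens to a subject who withdraws while positive: someone last swabbed, and positive, at 48 hours becomes a shedder of about two days after infusion.

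The SAP handles the same situation properly elsewhere. SAP 10.1 censors unresolved subjects at the last diary record and uses log-rank and Kaplan-Meier methods. SAP 10.2 uses Kaplan-Meier for normal activity, temperature and individual symptoms.

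The rule acts at both ends of the distribution. The slowest clearers are capped and the fastest are removed. Both pull the arm means together. Viral shedding is a listed secondary efficacy endpoint and is close to the mechanism of a neutralising antibody, so a compressed comparison would mislead a reader of these tables.

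**Working it through.** **1. The ceiling.** Day 8 is (8 − 1) × 24 = 168 h after the start of infusion, which matches the protocol. With the ±4 h window this is 164/24 = 6.83 to 172/24 = 7.17 days. The clock starts at the screening swab. Protocol 4.1 says of consent that "it must be within 24 hours before the administration of study drug", and study procedures follow consent, so I take 24 h as the longest lead time (an inference). The upper bound is (172 + 24)/24 = 8.17 days. The ceiling is therefore about 7 to 8.2 days from baseline.

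**2. Do suspicious-ADE swabs count?** Three passages point to no. SAP 10.2 says "Viral shedding (titers) of swab samples based on qPCR and cell culture will be evaluated at the scheduled collection times". Its opening paragraph names diary records and site temperature, but not swabs, as the ADE data added to time-to-event analyses. SAP 5.1 keeps unscheduled results out of summary tables. Two passages leave it open: SAP 5.1 has an exception for results needed to interpret the data, and SAP 12.9 puts ADE titers in the virus titer listings, which feed Tables 14.2.11.x. If they count, a subject flagged on Day 8 could reach (168 + 168)/24 = 14 days, and length of follow-up would depend on symptoms.

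**3. Size of the Day 8 effect.** The plan gives no expected shedding duration, so every distribution here is an assumption. Shedding times T were simulated, 400,000 per arm, with swabs at days 1, 2, 4 and 7. The SAP rule takes the last swab before T, among subjects with at least one positive. The comparator is the same rule with swabs continued every 3 days, which isolates the cut-off from swab spacing. Loss = 1 − (SAP difference / comparator difference). Differences are placebo minus active, in mean days.

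Weibull times, active median 0.7 × placebo median:

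| Shape | Placebo median | Placebo positive Day 8 | Continued swabs | SAP rule | Loss |
|---|---|---|---|---|---|
| 2.5 | 3 | 0% | 0.66 | 0.66 | 0% |
| 1.5 | 3 | 8% | 0.79 | 0.74 | 6% |
| 2.5 | 5 | 20% | 1.26 | 1.20 | 5% |
| 1.5 | 5 | 32% | 1.53 | 0.96 | 37% |
| 2.5 | 7 | 50% | 1.98 | 1.34 | 32% |
| 1.5 | 7 | 50% | 2.26 | 0.88 | 61% |
| 1.5 | 9 | 62% | 2.98 | 0.75 | 75% |
| 2.5 | 9 | 69% | 2.65 | 1.09 | 59% |

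Lognormal times. Day 8 positivity is 1 − Φ(ln(7/median)/log-SD):

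| Log-SD | Medians | Placebo positive Day 8 | Continued swabs | SAP rule | Loss |
|---|---|---|---|---|---|
| 0.3 | 5 vs 4 | 13% | 0.88 | 0.85 | 3% |
| 0.3 | 6 vs 4.5 | 30% | 1.36 | 1.22 | 10% |
| 0.5 | 5 vs 4 | 25% | 0.97 | 0.74 | 24% |
| 0.5 | 6 vs 4.5 | 38% | 1.54 | 1.00 | 35% |
| 0.5 | 7 vs 5 | 50% | 2.11 | 1.17 | 45% |
| 0.5 | 8 vs 6 | 61% | 2.16 | 0.93 | 57% |

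**4. Effect of dropping early clearers.** In the Weibull runs, keeping subjects with no post-baseline positive (at 0 days) raises the SAP difference by at most 0.08 day (0.88 to 0.96 at shape 1.5, median 7). The excluded share is unequal: 12% of placebo and 20% of active at shape 1.5, median 3.

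**5. Would a Kaplan-Meier median suffice?** Take the lognormal case 6 vs 4.5, log-SD 0.5, with the event at the first negative swab. The proportion still positive is 1 − Φ(ln(t/median)/0.5). At day 4 it is 0.79 vs 0.59; at day 7, 0.38 vs 0.19. Both curves cross 0.5 at day 7, so the medians tie at 7 days. The SAP medians tie too, at 4.0. The tie comes from the swab grid, but the curves themselves are clearly apart.

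**The case against.** The strongest reply is that duration is one of several shedding outputs. SAP 10.2 also tabulates percent positive at each visit including Day 8, change from baseline, AUC and mean titer. The Day 8 row shows by arm how many durations meet the ceiling, and no test or decision rule attaches to duration. This stands and limits the weight of the point, but it reveals the ceiling without correcting the duration tables.

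A reader might go further than the documents allow in four ways.

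- *Swabbing stops at Day 8 for everyone.* Only the routine schedule does; suspicious-ADE subjects are swabbed longer.
- *Any antiviral effect is understated, by a fixed fraction.* The loss is nil to small when few subjects are positive at Day 8, and no single range holds across plausible curves. If an active arm shed longer, the ceiling would hide an unfavourable result.
- *Dose selection is distorted.* Protocol 2.2 refers to effect size and efficacy in general, and SAP 1.1 ties effect size to time to resolution of symptoms and fever. Neither names shedding duration.
- *A Kaplan-Meier median cures it.* Step 5 shows that it need not.

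**Conclusion.** The point holds as a flaw in a descriptive secondary analysis that should be corrected. That right-censored values are treated as complete, and that early clearers are excluded, follows from the SAP text and needs no assumption. The size does need assumptions. Across the curves tried, the cut-off alone removes between 0% and 75% of the mean difference: 6% or less where placebo Day 8 positivity is 20% or below, and more than half in several cases at 50% or above. At intermediate positivity it depends on the shape of the curve (10% at 30% positive, 24% at 25% positive). Excluding early clearers adds a smaller compression. The actual Day 8 positivity, which the SAP already tabulates, will show where the trial falls.

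**What to change.** In SAP 10.2, replace the duration summary with time to cessation of shedding, separately for qPCR and cell culture:

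- Include all subjects positive at baseline, also those with no later positive swab.
- Use scheduled swabs only, and state that suspicious-ADE swabs do not enter.
- Take the end of shedding to lie between the last positive swab and the first negative swab after it.
- Right-censor subjects positive at their last scheduled swab, including those who withdrew while positive.
- Present the whole curve by arm, either interval-censored or Kaplan-Meier with the event at the first negative swab, with 95% confidence intervals and the number censored. Do not rely on the median alone.
- Keep the present duration as a listing or supportive row.

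The cost is SAP wording and replacement tables and curves, with no new swabs. The limits should be stated with the results: estimates resolve only to the swab grid, medians may tie or not be reached, and means beyond Day 8 cannot be recovered.

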6.5 Appropriateness of Measurements

The primary and secondary efficacy endpoints are consistent with the "Guidance for Industry: Influenza: Developing Drugs for Treatment and/or Prophylaxis" provided by the FDA. The Flu-iiQ™ used in this study is a validated questionnaire developed to evaluate the influenza symptoms.

The primary virology outcome, quantitative changes in viral shedding, is assessed using standard qPCR and cell culture methods.

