5.3 Analysis Populations

ITT and ITTI populations will be analyzed according to the randomized treatment groups and safety and PK populations will be analyzed according to the actual treatment groups.

- Intent-to-Treat (ITT) Population: defined as all subjects randomized to study drug. All subjects will be included in the ITT as randomized even if they do not receive treatment, except

Statistical Analysis Plan

for the following situation:

Subjects who are screening failures but are randomized in the IWRS by accident and do not receive any study drug will not be included in the ITT population.

- Intent-to-Treat Infected (ITTI) Population: defined as all randomized subjects with confirmed influenza A by quantitative Polymerase Chain Reaction (qPCR) or cell culture.
- Safety Population: defined as all randomized subjects receiving any amount (full or partial dose) of study drug, except for the following situation:
Subjects who do not receive study drug but receive normal saline solution will be included in the safety population and they will be analyzed in the placebo group.
- PK Population: defined as all randomized subjects with confirmed influenza A by qPCR or cell culture who received a complete dose of study drug, with at least one post-dose PK sample.

If infusion interruptions and/or infusion rate adjustments occur during the drug administration, the subject is still considered to have received a complete dose provided that the full calculated dose (45 mg/kg or 90 mg/kg) has been given at the end of the infusion.

The analysis populations will be used for the analyses as follows:

- ITT Population:
 - Demographic and baseline characteristics
 - Use of drugs for symptom relief
 - Secondary efficacy endpoints
- ITTI Population:
 - Demographic and baseline characteristics
 - Primary efficacy endpoint
 - Secondary efficacy endpoints
 - Genotype
 - Phenotype
- Safety Population:
 - Viral serology
 - Prior and concomitant medications
 - Study drug exposure
 - Safety endpoints
 - Immunogenicity
- PK Population:
 - Demographic and baseline characteristics
 - PK analysis
 - HI antibody

HI antibody, genotype and phenotype will be analyzed in the Follow-Up CSR only.

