8.2 Clinical Characteristics

The following continuous variables will be summarized using descriptive statistics by treatment group:

- Duration from onset of illness to study drug administration (hours): [Start date/time of study drug administration] – [Date/time of onset of illness]
- Influenza symptoms score at screening: Average scores of respiratory, constitutional, systemic and total symptoms
- Body temperature (°C) at screening

The following categorical variables will be summarized in contingency tables:

- Influenza subtype (Influenza A/H1, Influenza A/H3, Influenza A/H1 and H3, Unknown, NA)
- Influenza confirmed (by cell culture, qPCR, both, no)
- Rapid kit test results (positive, negative)

When influenza A virus load from qPCR has quantitative value or less than Lower Limit of Quantification (LLOQ), then influenza is confirmed. However, when influenza A virus load from cell culture has only quantitative value, then influenza is confirmed by cell culture.

Summary tables will be presented for ITT, ITTI, and PK populations. Also data will be listed for the ITT population.

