11.3.2 Genotype

Genotype results will be presented in data listing by treatment group and subtype (H1N1 HA, H1N1 NA, H3N2 HA, H3N2, NA) in ITTI population.

Screening (influenza A positive sample regardless of titer value) and the last influenza A positive sample in time with $> 4 \log_{10}$ vp/ml will be analysed.

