16. Sponsor-supplied or agreed in advance rapid influenza diagnostic test material will be used. And if there is available test result confirmed as influenza A prior to obtaining written informed consent and that result was from the influenza diagnostic test which is agreed with Sponsor in advance, that test result can be allowed. At screening, testing must be performed within 24 hours before study drug administration. Subjects with a negative test result by rapid diagnostic test, who have onset of symptoms within 48 hours (window of +12 hours is allowed) before study drug administration, can be rescreened only once.
17. The Investigator or designee will perform a symptom-directed physical examination (which should include, at a minimum, the examination of ear, nose, throat, sinuses, and lungs) and assessment for potential complications of influenza.
18. The subject will record the results of the Flu-iiQ™ in the diary.
 - Flu-iiQ™ will be recorded once by the subject at the screening visit and will be recorded twice a day (at approximately 12-hour intervals) from Day 1 to Day 8 (in the morning [between 6 and 10 AM, approximately] and in the evening [between 6 and 10 PM, approximately]).
19. Body temperature which a subject experiences in prior to screening will be collected and body temperature taken with any type of thermometer will be acceptable. However, from the screening period, Sponsor-supplied thermometer will be used.
 - Temperature will be measured by subject; It will be recorded twice a day (at approximately 12-hour intervals) from Day 1 to Day 8 (in the morning [between 6 and 10 AM, approximately] and in the evening [between 6 and 10 PM, approximately]).
 - Temperature will be measured by site personnel at site: at screening, Day 1 (prior to infusion), Day 2 (±4 hours), Day 3 (±4 hours), Day 5 (±4 hours) and Day 8 (±4 hours).
 - These will be used for assessment of endpoint.
20. Use of all medications, from 30 days prior to randomization and up until Day 110/EOS visit, will be recorded in the subject's eCRF.
21. AEs will be collected from the date the informed consent form is signed until Day 110/EOS visit.
22. EOS visit will be done at Day 110. But if a subject is early terminated from the study, EOS visit will be done to assess safety parameters at any time.

CONFIDENTIAL

37/62 page

Effective Date: 01-Aug-2018

Statistical Analysis Plan

Schedule of Assessments (Unscheduled Visits Subjects with Suspicious ADE)

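### The duration-of-viral-shedding tables leave out baseline-positive subjects who are negative on every post-dose swab, so they do not compare the randomised groups

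*SAP*

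**What the plan says.** Viral shedding is a listed secondary efficacy endpoint (Protocol 8.2.2, SAP 3.1), to be analysed on ITTI and ITT. SAP 10.2 adds a duration summary, defined as "Duration (in days) of viral shedding; from date/time of baseline assessment to last positive sample". The sentence that follows limits who is summarised: "Subjects with at least one positive sample after baseline will be included in the summary".

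The next item in the same list, the AUC of viral levels, takes a different set: subjects with "at least one post-baseline result (including BLQ (Below the Limit of Quantification) and negative values".

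The duration results go into SAP tables 14.2.11.1.1 to 14.2.11.2.2, by assay, labelled ITT and ITTI. ITTI is "defined as all randomized subjects with confirmed influenza A by quantitative Polymerase Chain Reaction (qPCR) or cell culture", with no requirement for a positive swab after dosing; ITT has none either. Post-dose swabs are scheduled on Days 2, 3, 5 and 8.

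The protocol sets no duration rule. Its section 8.5.2 plans titres and change from baseline, and section 6.5 says: "The primary virology outcome, quantitative changes in viral shedding, is assessed using standard qPCR and cell culture methods".

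**The concern.** Among subjects positive at baseline on an assay, whether a subject enters the duration table is decided by swabs taken after randomisation. The treatment is intended to turn those swabs negative, so the subjects removed are the ones who cleared fastest, and a drug that clears virus early loses more of its best responders than placebo does. What remains in each arm is a subset selected on outcome. The table labels nevertheless invite the reader to treat the comparison as randomised.

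Subjects never positive on an assay, for example those confirmed by qPCR but negative on culture, have no duration on it. The point does not concern them.

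There is a second, smaller gap at the other end. For a subject still positive at the last swab, the time to that swab is only a lower bound on duration. The SAP neither flags nor censors it.

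**Working it through.** **Reading the rule.** Take a subject positive at baseline and negative on all four post-dose swabs. The last positive sample is the baseline swab, so the SAP's definition gives duration 0. The inclusion sentence removes the subject, and nothing elsewhere in either document puts the subject back. The same subject counts in AUC tables 14.2.12.x.

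**Is there a figure to reproduce?** No. Neither document states a shedding duration or the share of subjects negative on all post-dose swabs. Everything below is illustrative and shows what can happen, not what is likely.

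**Inputs.**
- From the documents: swabs about 1, 2, 4 and 7 days after the start of infusion (Protocol 6.1.2); planned infected subjects, 38 placebo and 63 per CT-P27 arm (SAP 5.2).
- Assumed: Weibull clearance among baseline-positive subjects with shape k; placebo median m = 3 days; drug halves the median; baseline swab at dosing; 70–100% of ITTI subjects baseline-positive on the assay.

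**Formulas.** S(t) = exp(−ln2·(t/m)^k). The last positive swab falls on day 0, 1, 2, 4 or 7 with probability 1−S(1), S(1)−S(2), S(2)−S(4), S(4)−S(7), S(7).
- Mean over all baseline-positive subjects = Σ(day × probability).
- Mean under the SAP rule = that sum ÷ S(1).

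| | P(0) | P(1) | P(2) | P(4) | P(7) | Mean, all | Mean, SAP rule |
|---|---|---|---|---|---|---|---|
| Exponential (k=1), placebo | 0.206 | 0.164 | 0.233 | 0.198 | 0.198 | 2.813 | 3.544 |
| Exponential, active | 0.370 | 0.233 | 0.239 | 0.118 | 0.039 | 1.460 | 2.317 |
| Weibull (k=2), placebo | 0.074 | 0.191 | 0.443 | 0.269 | 0.023 | 2.313 | 2.498 |
| Weibull (k=2), active | 0.265 | 0.443 | 0.284 | 0.007 | 0.000 | 1.041 | 1.417 |

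P(0) is the share excluded and P(7) the share still positive at Day 8.

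- Exponential: the difference is 2.813 − 1.460 = 1.35 days over all subjects and 3.544 − 2.317 = 1.23 under the rule (91% kept).
- Weibull: 2.313 − 1.041 = 1.27 becomes 2.498 − 1.417 = 1.08 (85% kept).

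**Subjects removed.** Exponential: 0.206 × 38 = 7.8 placebo and 0.370 × 63 = 23.3 active if all are baseline-positive, or 5.5 and 16.3 at 70%. Weibull: 2.8 and 16.7, or 2.0 and 11.7.

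**Share of the difference kept, other assumptions.**

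| Placebo median | k=1 | k=1.5 | k=2 | k=3 |
|---|---|---|---|---|
| 2 days | 92% | 78% | 68% | 59% |
| 3 days | 91% | 88% | 85% | 85% |
| 4 days | 89% | 92% | 92% | 94% |

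At median 2, half the active arm is assumed clear by 24 h.

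**Earlier baseline swab.** If it is taken 24 h before dosing, 1 day is added to every non-zero duration. The all-subject mean rises by S(1); the rule mean rises by 1 in both arms, so its difference does not move.
- Exponential: 3.606 − 2.090 = 1.52 becomes 1.23 (81% kept).
- Weibull: 3.239 − 1.776 = 1.46 becomes 1.08 (74% kept).

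**Particular mechanisms, placebo median 3.**
- *Masking.* The drug moves a fraction f of subjects to clearance before 24 h, regardless of how long they would have shed, and leaves the rest unchanged. The true difference is f × placebo mean. For f = 0.1 to 0.4 that is 0.28 to 1.13 days (exponential) or 0.23 to 0.93 (Weibull). Under the rule it is 0.00 by construction.
- *Reversal.* The drug moves to before 24 h half of those who would clear between 24 and 96 h, and leaves slow shedders alone. Exponential: the active mean is 2.498 over all and 2.498/0.595 = 4.196 under the rule, so +0.31 becomes 3.544 − 4.196 = −0.65. Weibull: 1.774 and 1.774/0.609 = 2.914, so +0.54 becomes −0.42.

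**The case against.** The strongest reply is that little hangs on these tables. Duration is one of several descriptive shedding summaries, no test is named for it, and the protocol did not ask for it. Percent positive by visit and change in titre will still show early clearance. Baseline positivity by assay is tabulated, so a reader could subtract the duration n from the baseline-positive count and get close to the number of early clearers. In the main case 85–91% of the difference survives, and masking and reversal come from constructed mechanisms. A footnote saying the table is conditional on a post-baseline positive would make it accurate.

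Most of that stands as a limit on importance. It does not make the tables right. Neighbouring outputs do not correct a biased mean duration, the subtraction fails with missing swabs and late converters, and a footnote would describe the selection without removing it.

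Three narrower points also have some force.
- The 24-hour limit in SAP 14.1, footnote 16 ("At screening, testing must be performed within 24 hours before study drug administration") is for the rapid test. Footnote 1 puts consent within 24 hours of dosing, which gives a similar bound for the virology swab; the lag case is a sensitivity check only.
- Loss is probably smaller for qPCR than for culture if any qPCR detection counts as positive. The illustration does not separate the assays.
- A duration of 0 is partly an artefact of the swab schedule, since clearance came at an unknown time before Day 2. It is nevertheless what the SAP's own definition yields.

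**Conclusion.** The concern holds. The inclusion rule selects on a post-randomisation outcome, and whenever it excludes a baseline-positive subject the duration tables stop being comparisons of the ITT or ITTI groups. Equal exclusion shares in the arms would not by themselves restore comparability.

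Size and direction cannot be known from the documents. Under smooth clearance curves with placebo medians of 3 to 4 days and a halving by the drug, 85–94% of the true difference is kept; at median 2 it is 59–92%. Complete masking or a reversed sign needs a drug effect concentrated on early clearance.

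The scope is limited: a descriptive addition to a secondary endpoint, with the primary analysis and its power unaffected. SAP 1.1 rests dose selection on symptom and fever effect size, safety and PK; Protocol 2.2 also names efficacy. It merits correction before analysis but does not threaten the trial's main conclusion.

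**What to change.** In SAP 10.2, for each assay and in both the ITT and ITTI tables:

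1. Include every subject with a positive baseline swab on that assay and at least one post-baseline swab. Assign duration 0 when all post-baseline swabs are negative.
2. Flag or censor subjects still positive at their last swab. One option is a Kaplan-Meier analysis of time to the first negative with no later positive, counting all-negative subjects as events at the first post-dose swab. That is a different measure from time to last positive and should be labelled as such.
3. Report by arm how many subjects are not baseline-positive on the assay, including any who turn positive later. Keep the present rule only as a supplementary table, labelled as conditional.
4. State the rule for a positive swab, which the SAP now only implies. For qPCR, detection at any level: section 8.2 says "When influenza A virus load from qPCR has quantitative value or less than Lower Limit of Quantification (LLOQ), then influenza is confirmed", and the genotyping selection in 11.3.2 is in line with this ("Screening (influenza A positive sample regardless of titer value"). For culture, at or above the limit of quantification, since 10.2 treats values below 0.75 as negative.

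The cost is SAP wording and a little more table programming. No new samples are needed.
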